497 **Pelvic Organ Prolapse/Incontinence Sexual Questionnaire, IUGA-revised (PISQ-IR, women)** is a
498 validated measure of sexual function in women with pelvic organ prolapse, incontinence, and/or fecal
499 incontinence. (Appendix H)

500 **Pelvic Floor**

501 **Pelvic Floor Distress Inventory – short form (PFDI-20, women)** is a 20-item validated measure with three
502 subscales to assess pelvic floor symptoms in women, including urinary, prolapse, and colorectal.
503 (Appendix I)

504 **Pain**

505 **Genitourinary Pain Index (GUPI)** is a 9-item measure to assess GU pain in men and women. (Appendix J)

506 **Pediatric Disorders**

507 **Childhood Traumatic Events Scale** is a 6-item measure assessing recollection of events associated with
508 major upheaval such as deaths. (Appendix K)

509 **Psychosocial Symptoms**

510 **PROMIS Depression and Anxiety item banks** measure mood, affect, negative self-perceptions, negative
511 social perceptions, fear, anxious feelings, hyperarousal, and somatic symptoms related to arousal.
512 (Appendices L and M)

513 **Perceived Stress Scale (PSS)** contains 10 items and assesses non-specific subjective stress. (Appendix N)

514 **PROMIS Sleep Short Form** is a validated 8-item assessment of sleep patterns. (Appendix O)

515 **General Health-Related Quality of Life**

516 **International Physical Activity Questionnaire – Short Form (IPAQ-SF)** is a 9-item assessment of four
517 levels of activity. (Appendix P)

518 **PROMIS Physical Function Item Bank, Mobility Subdomain** consists of 16 items that measure lower
519 extremity function. (Appendix Q)

520 **3.4.8 Biosample Collection**

521 Blood, urine, and saliva will be collected in all participants at the baseline visit and at the 3 and 12
522 month visits. Swabs will be collected at the baseline visit. For men, a cotton-tipped swab will be used to
523 culture the perineal area. For women, a cotton-tipped swab will be used to culture the vaginal opening.

524 All biosamples will be collected according to methodologies outlined in the Manual of Operations. All
525 biosamples will be stored at the NIDDK Sample Repository for future use, including targeted
526 phenotyping studies.

527 **3.4.9 Sample Size and Power Calculations**

528 Estimates of numbers of patients with LUTS who would be available for recruitment into the prospective
529 observational cohort have been provided by investigators at the six LURN clinical sites, and are shown in
530 Table 3.

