1664 study involved only 35 patients with inflammatory bowel disease. The authors determined the gene
1665 expression profiles of patients and blindly binned them into different subgroups based upon their
1666 expression levels using unsupervised clustering techniques. After the biomarker groups were
1667 determined, the biomarker phenotypes were compared with clinical outcomes. Interestingly, the
1668 clusters were able to predict clinical outcomes. Taken together, these studies demonstrate how a
1669 “biomarker-driven approach” can be used to define clinical phenotypes.

1670 5.3 Rationale

1671 Before embarking upon a large-scale project, several questions and concerns need to be answered. For
1672 example, it is currently unknown whether SomaScan can be used to measure proteins that are relevant
1673 to LUTS. As such, it is important to determine if there are differences in the concentrations of proteins in
1674 patients with LUTS compared with those without LUTS symptoms.

1675
1676 While previous studies have identified proteins contained within plasma and urine that are associated
1677 with the presence and severity of LUTS, the ideal biologic specimen for this purpose remains unknown.
1678 Therefore, it would be prudent to determine the best biospecimen medium (plasma vs. urine) that will
1679 provide the most robust results.

1680
1681 Finally, while biospecimens have been collected as part of the LURN Observational Cohort, before a
1682 large-scale study is performed it will be important to verify if the samples were appropriately collected
1683 by Research Sites for SomaScan assay.

1684 Although SomaScan was used in multiple biomarker studies of complex common diseases, it has not
1685 been applied towards patients with LUTS. Therefore, prior to using this methodology in a large-scale
1686 study, we will perform a pilot project, to inform the design of a future study. In this pilot study, we plan
1687 to assess the feasibility of conducting a larger-scale study by:

[figure not shown]
- 1688 • determining the ideal media for measuring proteins related to LUTS (plasma, urine, or
1689 both)

- 1690 • estimating the number and effect size of biomarkers in a LUTS signature group
- 1691 • estimating covariance matrices of SomaScan targets in LUTS patients and in controls
- 1692 • evaluating the reproducibility of SomaScan assay by using blind duplicates of the
- 1693 samples

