- 1694 • evaluating the quality of sample collection/storage at each of the six LURN Research
- 1695 Sites

1696 5.4 Materials and Methods

1697 A schematic overview for the pilot project is presented in Figure 6.

1698
1699 **Figure 1: Pilot Biomarker Study Flowchart**

1700

1701 5.5 Participant Selection

1702 For this study, females with LUTS (n=18) and males with LUTS (n=18) that are enrolled in the LURN
1703 Observational Cohort Study will be blindly and randomly selected (3 males and 3 females from each
1704 participating LURN site) from individuals with severe LUTS symptoms (at least one symptom with
1705 severity level 4 or higher, as justified in Section 4.3.3). 24 evaluable controls, (12 females and 12 males),
1706 without LUTS will also be recruited for this study (see Inclusion and Exclusion criteria below). Controls
1707 will be frequency matched with cases by age, sex, race, body mass index (BMI), diabetes status, and
1708 LURN institutional site. Controls should not have significant LUTS, but are not required to be completely

1709 healthy. Exclusion criteria for controls are the same as exclusion criteria for LURN patients, plus the
1710 presence of LUTS. The detailed inclusion and exclusion criteria for controls are presented in Section
1711 4.1.2. Plasma and urine samples for selected cases will be requested from the NIDDK Biorepository. In
1712 order to evaluate SomaScan reproducibility, one female and one male case and one female and one
1713 male control subjects will be randomly selected. For each of these controls, 3 additional aliquots will be
1714 prepared and labeled in a way that does not allow identifying them as duplicates. These blind duplicate
1715 samples will be added to the whole collection of samples (18 female LUTS patients + 18 male LUTS
1716 patients + 12 female controls + 12 male controls + 12 blind duplicates = 72). The total of 72 plasma and
1717 72 urine samples will be analyzed with SomaScan at SomaLogic, Inc. The proposed numbers of cases and
1718 controls in the pilot study are based on literature recommendations^[21, 22, 23, 24] for the sample size in
1719 pilots, which vary from 10-15 per group to 24-36 per group, but are generally not more than 10% of the
1720 planned larger-scale study.

1721
1722 We will record the quality of ongoing biospecimen collections for LURN by obtaining the details
1723 surrounding the specimens being used in this pilot study (e.g., timing of collection, time required to

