1724 place at -80 degrees, etc.). Only samples that have been processed within 2 hours from collection will be
1725 used for this study. We will send the biospecimens to SomaLogic for analysis on the SomaScan. The
1726 SomaScan will be used to analyze a protein panel of 1310 proteins contained within the plasma and
1727 urine. Results will be sent directly to the LURN data coordinating center (DCC). Data derived from
1728 plasma and urine will be handled independently.

1729 **5.6 Methodology**

1730 **5.6.1 Evaluation of reproducibility of SomaScan**

1731 We will evaluate the reproducibility (measurement error) of a SomaScan assay by performing it on blind
1732 replicates of plasma and urine samples from two different control subjects and two different LUTS
1733 subjects. We will randomly select male and female cases and controls and will send for blinded analysis
1734 the original sample, plus three additional aliquots for each of these subjects. If possible, we will send
1735 these in different batches to include both intra- and inter-assay variability in the assessment of
1736 reproducibility. The presence of four replicates for each of the two cases and two controls will enable us
1737 to estimate the standard deviation, mean, and coefficient of variation (CV) for both controls for each of
1738 the 1310 biomarkers. These CV estimates will be compared with the distribution of CV levels across the
1739 biomarkers (median 4.6%, interquartile range 3.9% to 7.3%) advertised by SomaLogic and provided in
1740 their SOMAscan™ Proteomic Assay Technical White Paper available online
1741 (<http://www.somallogic.com/Technology/SOMAscan-basic-info.aspx>).
1742

1743 **5.6.2 Evaluation of the quality of sample collection/storage**

1744 Strict adherence to the sample collection and storage procedure (for plasma not more than 2 hours
1745 from hand to -80 refrigerator) is crucial for the success of SomaScan assay. Output of the SomaScan
1746 assay is a 1310-dimensional vector with each dimension characterizing abundance of one of 1310 target
1747 proteins in a given patient sample. Length of this vector:

$$L_i = \sqrt{\sum_{j=1}^{1310} A_{ij}^2}$$

1748 (i-subject index, j-protein index, A_{ij} -abundance of protein “j” in the sample of patient “i”)
1749 represents overall protein abundance for each patient sample. If L_i is substantially smaller for the patient

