- 2003 Urine has great utility as a testing matrix. It is easily accessible, can be collected noninvasively, and
 2004 provides information on numerous physiological processes. Urine is a source of numerous potential
 2005 biomarkers, including metabolites, cells, proteins, and nucleic acids. To be used successfully for
 2006 biomarker discovery and validation, various urine specimen parameters must be harmonized, including
 2007 collection method, volume collected, and timing of collection, processing, and storage. As such, we have
 2008 previously outlined standard methodology for urine collection (refer to Biomarker Collection section of
 2009 the LURN Phenotyping Study Protocol Manual of Operations [MOO]). This is briefly summarized below:
- 2010 1) Either a catheterized specimen or a spontaneously voided mid-stream specimen will be
 - 2011 obtained from female patients, depending on provider practice. Male patients will provide
 - 2012 spontaneously voided mid-stream specimens.

- 2013 2) A total volume of 50-100ml will be collected, and aliquots of uncentrifuged urine will be
2014 obtained.
2015 3) Urine will be processed as described in the MOO.

2016 **5.11.5 Blood Collection for Controls**

2017 Blood and its components are commonly used as a testing matrix associated with minimal risks to study
2018 participants. Controls enrolled in this pilot study will be asked to donate blood for analysis. It is
2019 recommended that controls will be fast for 8 hours prior to blood draw unless it is medically
2020 contraindicated. The time of the last meal and the time of blood draw will be recorded. Standard
2021 protocols for blood collection have been developed and are described in detail in the Observational
2022 Cohort Study MOO. Briefly, we will collect blood for serum and plasma studies. Plasma samples will be
2023 collected according to the manufacturer's (SomaLogic, Inc.) protocol and processed as recommended.
2024 All plasma will be processed and stored at -80 degrees Celsius within 2 hours from collection.
2025

2026 **6 Human Subjects**

2027 **6.1 Protection of Human Subjects**

2028 **6.1.1 Institutional Review Board**

2029 This study and analysis will be performed under Institutional Review Board (IRB) oversight. Prior to the
2030 initiation of the study, an IRB approval for study of human subjects will be obtained separately from the

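### The rule admitting plasma to the biomarker pilot stops the 2-hour clock at processing, while the limit the protocol calls crucial for the assay stops it at -80 storage

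*Protocol*

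**What the plan says.** Four parts of the protocol bear on the time limit.

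- **Section 5.11.5 (blood collection for controls):** "All plasma will be processed and stored at -80 degrees Celsius within 2 hours from collection". Processing and storage are named as two steps, and both must be finished by 2 hours.
- **Section 5.6.2 (quality of collection and storage):** "Strict adherence to the sample collection and storage procedure (for plasma not more than 2 hours", continuing "from hand to -80 refrigerator) is crucial for the success of SomaScan assay". This applies to plasma without distinguishing cases from controls.
- **Section 5.5 (participant selection):** "Only samples that have been processed within 2 hours from collection will be" used in the pilot. Freezing is not mentioned. Just before this, the section lists the time taken to "place at -80 degrees, etc" among the details to be recorded for the specimens used.
- **Section 3.4.8 (biosample collection in the cohort that supplies the cases):** "All biosamples will be collected according to methodologies outlined in the Manual of Operations". It gives no time limit of its own.

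On the source of the case material, section 5.5 says "Plasma and urine samples for selected cases will be requested from the NIDDK Biorepository". Controls are recruited after the cases have been selected (section 5.11.2). Section 5.3 treats the suitability of the cohort samples as still open: before a "large-scale study is performed it will be important to verify if the samples were appropriately collected" by the sites for this assay.

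**The concern.** A threshold described as crucial should be the one that governs entry to the assay. Here the entry rule names an earlier event, processing, and leaves the interval from processing to the freezer unrestricted. The recorded freezer time that could close the gap has no stated use.

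The gap need not fall equally on the two groups. Control plasma is collected prospectively under an explicit instruction to reach -80 within 2 hours. Case plasma is taken from the repository, and for it the section 5.5 filter is the only check the protocol states at the point of use. If freezing delay changes the measured abundance of some proteins and delay is commoner among cases, part of a case-control difference would reflect handling.

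That contrast feeds most of what the pilot is meant to deliver: the count of differentially abundant proteins and their effect sizes (5.6.3), the choice between plasma and urine (5.6.4 and 5.7), and the sample size for the larger study (5.6.5). Section 5.6.5 also keeps open the option of combining the pilot data with the larger study.

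**Working it through.** The protocol states no figure that can be reproduced for this point. The check is a comparison of texts, followed by a look at what could catch a late sample.

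**1. End points side by side**

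| Section | Applies to | 2-hour clock ends at |
|---|---|---|
| 5.11.5 | Control plasma, at collection | Processed and stored at -80 |
| 5.6.2 | Plasma generally | -80 freezer |
| 5.5 | All pilot samples, at admission | Processed |
| 3.4.8 | Cohort biosamples, including cases, at collection | No limit stated; defers to the manual |

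**2. Test case.** Take plasma processed at 1 h 50 min and frozen at 2 h 30 min (times chosen for illustration).
- Section 5.5: 1 h 50 min is under 2 h, so it is admitted.
- Section 5.6.2: 2 h 30 min is over 2 h, so it misses the limit by 30 min.
- Section 5.11.5: if it is a control sample, its collection rule was also broken, yet section 5.5 still admits it.

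**3. What might catch it**
- *Recorded time to -80 (5.5).* It would identify the sample, but no action follows from it.
- *Vector-length check (5.6.2).* This compares overall protein abundance between sites, not between cases and controls. Its stated consequence is a re-examination of the site's procedures, not removal of samples. Because it summarises all 1310 proteins in one length, it need not show a change confined to a few.
- *Matching (5.5).* Controls are frequency matched on age, sex, race, BMI, diabetes and site. Site matching limits confounding by differences in handling between sites. It does not address a difference between banked and newly collected samples within a site.

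None of these closes the gap in the admission rule.

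**4. What an effect would require.** The protocol gives neither the share of case samples frozen late (f) nor the relative change that late freezing causes in a protein (c). Both are assumptions here. Suppose there is no true LUTS effect, all control plasma is on time and only cases are affected. The case mean then moves by f x c. Section 5.6.3 counts a protein as differentially abundant when it differs by more than 30%, so a comparison of group means reaches that threshold when

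f x c = 0.30

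For example, f = 0.30 needs c = 1.0 (a doubling), since 0.30 x 1.0 = 0.30; f = 0.60 needs c = 0.5, since 0.60 x 0.5 = 0.30. This shows what would have to be true; it does not estimate a bias.

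**5. Room for a stricter rule.** Cases needed: 3 per sex per site x 2 sexes x 6 sites = 36. Section 5.11.1 reports that 60% of men and 74% of women recruited by 2 December 2015 met the severity criterion. If those shares held at the planned 500 of each sex, the pool would be 0.60 x 500 = 300 men and 0.74 x 500 = 370 women, for 18 places each. For controls, section 5.11.2 anticipates up to 24 + 24 = 48 recruited for 24 places.

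**The case against.** The strongest reply is that this is one limit worded loosely, with no separate standard for cases. Several parts of that reply stand.

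- Section 5.6.2 sets the -80 end point for all plasma, so the protocol does not exempt cases from it.
- Section 5.5 covers controls too. A control sample frozen late would also be admitted.
- Section 5.11.5 says it summarises procedures set out in the cohort study's own manual, which is where section 3.4.8 sends case collection. Cases and controls may share one blood procedure. The manual is not shown, so this can be neither confirmed nor ruled out.
- The sentence before the admission rule mentions time to -80, so 'processed' may be shorthand for the whole interval.

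The shorthand reading does not settle the matter. Section 5.11.5 lists processing and storage as distinct steps, and an admission rule has to be applied by people who will read it literally. A shared procedure would also not show that the banked samples complied with it, and section 5.3 leaves that to be verified.

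A reader might go further and infer that late freezing occurs only among cases, so that its effect cannot be separated from LUTS. The documents do not support this. Nothing says control samples are never late, and because freezer times are recorded, late samples could be identified and set aside, leaving on-time cases to compare with on-time controls. Nor can a false-positive rate from a two-group significance test be attached to the point: section 5.6.3 plans a 30% abundance rule and a rough effect size, not such a test.

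**Conclusion.** The inconsistency is real. The operative rule in section 5.5 admits plasma that fails the limit section 5.6.2 calls crucial, and no stated rule acts on the recorded time to -80.

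The consequence for the case-control contrast is a possibility, more likely to arise through banked cases than through prospectively collected controls. It rests on three assumptions that the protocol does not settle: that some banked case plasma reached -80 after 2 hours, that this was commoner than among controls, and that the delay alters some measured proteins. The direction and size of any bias cannot be derived.

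The point concerns plasma only; the hand-to-freezer limit is not stated for urine. It does not undermine the pilot's design, but it should be corrected before samples are drawn, since the threshold decides what is assayed and the change is small.

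**What to change.** - **Section 5.5:** for plasma, require that the sample was both processed and placed at -80 no later than 2 hours after collection, for cases and controls alike. Leave the urine rule as it is. Sections 5.5, 5.6.2 and 5.11.5 then state one end point.
- **Timing:** apply the rule to recorded freezer times before the random draw of cases and before the control samples are selected. The draw then remains random among eligible participants.
- **Reporting:** show the distribution of time to -80 by case/control status beside the protein comparison.

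The cost is one line of text and a check of freezer times in the candidate pool. Section 5.5 plans to obtain these times for the specimens used, so they would have to be retrieved earlier and for more samples; whether they are held for every banked sample is not stated. Somewhat fewer banked samples will be eligible. The places to fill are few (three per sex per site for cases, and 24 control samples from up to 48 controls), so the loss should be tolerable unless late freezing was common at a particular site. The check itself would reveal that.

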2269 submission. The DCC is responsible for clinical monitoring of the study.

2270 Arbor Research Collaborative for Health
2271 Ann Arbor, MI
2272 Principal Investigator: [name], FACS

2273 **7.3 Steering Committee**

2274 The primary governing body of the study is the Steering Committee, consisting of each of the Principal
2275 Investigators of the LURN clinical study centers, the Principal Investigator of the DCC, and the NIDDK
2276 Project Scientist. The Steering Committee develops policies for the study pertaining to access to patient
2277 data, performance standards, and publications and presentations. It develops the study protocol and
2278 meets to discuss the progress of the study and to consider problems arising during its conduct. The
2279 Steering Committee may establish subcommittees to further develop specific components of the study
2280 protocol. Small working groups may be established to prepare manuscripts and presentations.

2281 **8 Study Management**

2282 **8.1 Data Collection, Data Collection Forms, Data Entry**

2283 The DCC will utilize the Web-based ArborLink as the data management nucleus for the LURN
2284 phenotyping studies. ArborLink is a database platform developed by Arbor Research Collaborative for
2285 Health (Arbor Research). The DCC will utilize ArborLink to create electronic case report forms to capture

2286 all relevant study data for the core study and all investigational/research protocols that are developed
2287 and implemented during the course of LURN. The ArborLink system allows real-time monitoring of study
2288 data for protocol adherence, quality assurance, adverse event reporting, discrepancy reporting, and
2289 other trends.

2290 **8.2 Data Management**

2291 Study data for Project 1a and 1c will be entered into the electronic data entry system by study
2292 coordinators at each study site. These data will be encrypted and transferred to the DCC and stored on a
2293 secure server at Arbor Research. Access to the server and data entry system is limited and requires a
2294 unique username and password combination. The servers are backed up daily and physically stored in a
2295 locked facility.

2296 Study data for Project 1b will be collected in three ways. DTI and RSfMRI will be transferred from each
2297 site to the central imaging data repository for quality assurance and central reading (see Section 4.3.1).
2298 Data will then be sent to the DCC for incorporation into the final study-wide data sets and for analysis.
2299 Pressure pain sensitivity data will be saved on local MAST servers at each site and transferred to the DCC
2300 using a secured SSH file transfer server. Auditory sensitivity data and additional study data (such as
2301 protocol deviations and timing of study procedures) will be entered into ArborLink by study coordinators
2302 at each study site.

2303 All analysis of the data sets will utilize de-identified (coded) data sets.

2304 **8.3 Quality Control and Database Management**

2305 The first steps in ensuring protocol compliance are good protocol design and careful orientation of study
2306 personnel. Following final agreement on protocols, and prior to study initiation at any of the LURN
2307 clinical study centers, the DCC will organize a Training and Certification session for LURN study
2308 coordinators/data entry personnel.

2309 The electronic data entry system will have built-in data checks as part of study quality assurance.
2310 Protocol compliance will be assessed by monitoring the submission of data at required intervals. Data
2311 inconsistencies and discrepancy reports will be reviewed by the Clinical Monitors so that necessary
2312 queries can be generated and sent to the LURN clinical study centers for verification and resolution.

2313 Periodic requests may be generated for the submission of random source documents to assess the
2314 quality of data acquisition and data entry at each site. In addition, the Clinical Monitor or Project
2315 Manager will visit each site at least once a year to review source documents, monitor regulatory
2316 compliance, and assess protocol adherence.

2317 In addition to source document verification, the Clinical Monitor and Project Manager will produce
2318 reports from the database to look for inconsistencies in submitted data, particularly for repeated
2319 measures data elements, even if data do not fall outside of built-in validation routines.

2320 Studies of intra-subject and inter-subject data variability by LURN clinical study center as well as intra-
2321 center and inter-center data variability will be used to further ascertain random or systematic data
2322 quality issues.

2323 **8.4 Data Security/ Data Transfer**

2324 For the Observational Cohort Study, personnel at each study center will collect and enter data into the
2325 Web-based data entry system. The following data security contingencies are in place:

- 2326 • Compliance with Industry Standards Regarding Data Security (HIPAA and 21 CFR Part 11)

- 2327 • Audit trails are maintained for all activity and all changes to any data element
- 2328 • All servers, Web servers, firewalls, etc. are configured and maintained according to industry best
2329 practice guidelines for backup, security, continuity of operations, and protection of PHI
- 2330 • All data are available only to authorized users from each site after secure login with encryption,
2331 with all site activity audited at the user level
- 2332 • All transmissions between the Internet and the database are encrypted using a 128-bit
2333 encryption algorithm
- 2334 • There is a comprehensive security plan in place
- 2335 Detailed instructions on the use of the database platform, data element definitions, and a code list will
2336 be provided in a MOO. Each study site will be provided a copy of the MOO and the entire manual will be
2337 available on the study website, and in the Help area of the database user interface.
- 2338 **8.5 Resource Sharing Plan**
- 2339 During the study, data and biosamples will be shared with internal and external investigators according
2340 to the guidelines agreed upon by the Steering Committee.
- 2341 Upon study completion, study data and materials will be transferred to the NIDDK Data Repository.
2342 Minutes of the meetings of the Steering Committee, Project Executive Committee, subcommittees, and
2343 the External Expert Panel will be kept on file at the DCC.
- 2344 Whole blood for creation of cryopreserved lymphocytes and biosamples collected during the study will
2345 reside at the NIDDK Genetics and Biosample Repositories.

9 References

- 2346
- 2347
- 2348 1. Andersson, K. and A. Wein, *Chapter 68: Pharmacologic Management of Lower Urinary Tract*
2349 *Storage and Emptying Failure*, in *Campbell-Walsh Urology, 10th edition*, K. LR, et al., Editors.
2350 2011.
- 2351 2. Coyne, K. S., L. S., Matza, Z. S. Kopp et al, *Examining lower urinary tract symptom constellations*
2352 *using cluster analysis*. BJU Int, 2008. **101**(10): 1267-73.
- 2353 3. Gong, X. and M. Richman, *On the application of cluster analysis to growing season precipitation*
2354 *data in North America east of the Rockies*. J of Climate, 1995. **8**(4): p. 897-931.
